5.2 Planned Dosage and Duration of Treatment

5.2.1 Dosage and Administration

^{18}F -AV-1451:

All subjects will receive a single IV bolus administration of approximately 370 MBq (10 mCi) of ^{18}F -AV-1451 Injection.

Florbetapir F 18:

Subjects will receive a single IV bolus administration of approximately 370 MBq (10 mCi) of Florbetapir F 18 Injection.

5.2.2 Rationale for Dosage

^{18}F -AV-1451 will be administered IV in a radioactive dose of 370 MBq (10 mCi) with a maximum human dose (MHD) limited to 20 μg of compound by weight. This dose is 150 fold lower than the NOAEL observed in the rat single dose toxicity study and is 50 fold lower than the NOAEL observed in the rat and dog repeat dose toxicity studies.

Human dosimetry has been obtained in nine subjects. The results estimated an Effective Dose of 8.92 mSv for an anticipated 370 MBq (10 mCi) injection and is comparable to the effective dose of approved ^{18}F -labeled compounds such as FDG and florbetapir F 18 injection.

The proposed dose has been shown to have acceptable image quality in previous human studies. No treatment related adverse events have been reported using this regimen.

5.3 Selection of Subjects

5.3.1 Inclusion Criteria

All subjects must meet all of the following criteria to enroll in this trial:

1. Males that have consented, are currently enrolled in the PFBHS protocol, and have participated in a minimum of 10 professional fights;
2. Can tolerate PET scan procedures; and
3. Have the ability to provide informed consent for study procedures (if the patient is ineligible to give informed consent, based on local standards, the patient's legal representative may consent on behalf of the patient, but the patient must still confirm assent).

Subjects with cognitive impairment should meet the following criteria:

1. Have subjective cognitive complaints or objective decline or impairment as determined by the investigator.

5.3.2 Exclusion Criteria

Subjects will be excluded from enrollment if they:

1. Have behavior dysfunction that is likely to interfere with imaging. The investigator should carefully consider whether subjects with behavior dysfunction will be able to complete the imaging session(s) and may be enrolled only after discussion and with approval of the sponsor;
2. Are claustrophobic or otherwise unable to tolerate the imaging procedure (use of mild sedatives are permitted to manage claustrophobia);
3. Have current clinically significant cardiovascular disease, or clinically significant abnormalities on screening ECG (including but not limited to QTcF>450 msec. Subjects with QTcF>450 msec in the presence of bundle branch block may be enrolled after discussion with sponsor);
4. A history of additional risk factors for Torsades de Pointes (TdP) (e.g., heart failure, hypokalemia, family history of Long QT syndrome) or are taking drugs that are known to cause QT-prolongation (a list of prohibited and discouraged medications is provided by the Sponsor);
5. Have a current clinically significant infectious disease, endocrine or metabolic disease, pulmonary, renal or hepatic impairment, or cancer that the investigator believes would affect study participation or scan results;
6. Have had a non-study related radiopharmaceutical imaging or treatment procedure within 7 days prior to the ¹⁸F-AV-1451 imaging session;
7. Have current drug or alcohol dependence or alcohol dependence within the past 2 years; and
8. In the opinion of the investigator, are otherwise unsuitable for a study of this type.

5.4 Prior and Concomitant Therapy

Except as noted in the exclusion criteria, all medications (prescription or over-the-counter) that have been started prior to screening may be continued during the course of the trial. All medications, including investigational medications that are continued from the start of the trial, or that are started during the trial (other than the study medication), must be documented on the Concomitant Medication Page of the electronic Case Report Form (eCRF).

5.5 Removal of Subjects from Trial

Subjects must be removed from the trial if:

1. Informed consent is withdrawn; or
2. The investigator or the sponsor believes it is in the best interest of the subject to be removed from the trial.

Subjects may be withdrawn from the trial if a SAE occurs. The date and reason for discontinuation should be noted on the eCRF. Subjects who discontinue prematurely should be seen for a final evaluation.

5.6 Premature Termination of Trial/Closure of Center

The sponsor may discontinue the trial at any time. Reasons for discontinuation of the trial may include, but are not limited to, new information on safety or efficacy, requests from regulatory authorities, or changes in business priorities. Additional reasons for center closure may include, but are not limited to, excessive protocol violations, inadequate regard for subject safety, failure to follow recommended procedures (e.g., documentation), failure or inability to accommodate Avid/Contract Research Organization (CRO) monitors or to provide required access to data and source documents, staff turnover, inadequate staffing, and inadequate enrollment. Except in cases affecting subject safety, the investigator may complete final study evaluations for ongoing subjects. In all cases of center, or study termination, appropriate steps will be taken to ensure the safety of study subjects.

6. WARNINGS/PRECAUTIONS

The most up-to-date and complete information regarding the use of ¹⁸F-AV-1451 Injection can be found in the investigator's brochure.

In brief, ¹⁸F-AV-1451 Injection is an experimental imaging agent that will be used at relatively low (tracer) doses. Because ¹⁸F-AV-1451 Injection is under clinical investigation, it is recommended that subjects receiving ¹⁸F-AV-1451 Injection be followed closely by means of adverse event reporting.

There are no data on the effects of ¹⁸F-AV-1451 Injection in human perinatal development. For this reason, males enrolled in this study must agree to use adequate contraceptive methods, if they engage in sexual activity for at least 90 days after administration of ¹⁸F-AV-1451 Injection.

7. PROCEDURES AND METHODS

7.1 Assessment Periods (See Section 11.2, Trial Flow Chart)

The study will consist of the following sequence of activities:

7.1.1 Screening Visit:

Subjects currently enrolled in the PFBH study protocol will be contacted to participate. Screening assessments may take place over several days, within 90 days of the ^{18}F -AV-1451 PET scan, and will include:

- Informed Consent will take place before any ^{18}F -AV-1451-A11 study procedures;
- Demographics (birth year, gender, race, ethnicity, education, alcohol, drug use and smoking);
- Medical history and concomitant medications;
- Safety assessments: Vital signs (pulse rate, respiratory rate, supine blood pressure, height and weight), ECG (with results reviewed prior to ^{18}F -AV-1451 administration), and safety labs (hematology, chemistry and urinalysis) including plasma thiamine (vitamin B1) level;
- Mini-Mental State Examination (MMSE);
- Digit span forward and backward;
- Beck Depression Inventory II;
- If a volumetric MRI has not been performed as part of PFBHS within six months of the ^{18}F -AV-1451 PET imaging visit, a volumetric MRI is to be performed as part of this study’s screening assessments; and
- A physician will see the subject during the screening assessments.

7.1.2 *Imaging Visit(s)*

^{18}F -AV-1451 PET Imaging Visit

- A physician or a licensed/credentialed medical professional (i.e., a PET technologist, imaging center nurse or a regional equivalent) designated by the site principal investigator must assess or evaluate the subject prior to administration of ^{18}F -AV-1451 Injection to determine if they are still suitable to undergo the scan. If a designee performs this activity, a physician must be available to provide medical consultation;
- Vital signs will be taken (pulse rate, respiratory rate, supine blood pressure) at the following time points:
 - Prior to administration of ^{18}F -AV-1451 Injection (Weight will also be collected)
 - Within 5 minutes after completion of injection of ^{18}F - AV-1451 Injection
 - After completion of the PET scan prior to discharge;
- Subjects will receive a single IV bolus injection target dose of 370 MBq (10 mCi) of ^{18}F -AV-1451 Injection followed by a saline flush.
- At approximately 75 minutes following injection, a continuous 30-minute brain scan will begin;
- The injection site will be observed for excessive inflammation or damage to the surrounding tissue where the dose was injected;
- Adverse events will be continuously monitored during the ^{18}F -AV-1451 PET imaging visit. Subjects who experience an adverse event will not be

discharged from the imaging center until the event has resolved or stabilized;

- A physician or a licensed/credentialed medical professional (i.e., a PET technologist, imaging center nurse or a regional equivalent) designated by the site principal investigator must assess or evaluate the subject prior to discharge from the imaging center to evaluate the subject’s readiness for discharge. If a designee performs this activity, a physician must be available to provide medical consultation; and
- A follow-up phone call to the subject, or informant where applicable, will be conducted within 2 or 3 business days of the imaging day, but not before 48 hours post-injection, to confirm subject well-being and to collect information about any new adverse events. If both of these days are not business days, the follow-up phone call can occur the following business day.

Florbetapir F 18 PET Imaging Session

All professional fighters ≥ 50 years of age and other participants in whom, and in the opinion of the investigator, the clinical presentation suggests a possible diagnosis of AD will return to the clinic for a florbetapir F 18 PET imaging visit. The PET imaging visits must be performed no more than 60 days apart.

- A physician, or physician designee, must see the subject prior to administration of Florbetapir F 18 Injection to determine if they are still suitable to undergo the scan;
- Vital signs will be taken (pulse rate, respiratory rate, supine blood pressure and weight) immediately prior to injection of florbetapir F 18;
- Subjects will receive a single IV bolus injection target dose of 370 MBq (10 mCi) of florbetapir F 18 followed by a saline flush;
- At approximately 50 minutes following injection, a continuous 10-minute brain scan will begin;
- Adverse events will be continuously monitored during the Florbetapir F 18 PET imaging visit. Subjects who experience an adverse event will not be discharged from the imaging center until the event has resolved or stabilized;
- A physician, or physician designee, will see the subject prior to discharge from the imaging center to evaluate the subject’s readiness for discharge; and
- A follow-up phone call to the subject, or informant where applicable, will be conducted within 2 or 3 business days of the imaging day, but not before 48 hours post-injection, to confirm subject well-being and to collect information about any new adverse events. If both of these days are not business days, the follow-up phone call can occur the following business day.

7.2 Observations and Measurements

Informed Consent

Potential subjects will be allowed to read a written informed consent form. The principal investigator, or designee, will explain all study procedures, risks, and alternative therapies to the subject. The subject will have an opportunity to have all questions answered. The appropriate parties will then sign and date the informed consent form, indicating willingness to participate in the study (see Section 7.5). A copy of the signed informed consent will be given to the subject.

All informed consent forms must be approved by Avid or designee, and by the appropriate Institutional Review Board (IRB) prior to use.

Medical History

The investigator or designee will obtain an updated history at the screening visit.

- Relevant demographic information
- Review of body systems
- Social history
- Medical and surgical history, including medical care for head trauma
- Concurrent medications

Whenever possible, the medical history will be confirmed by medical records.

Vital Signs

Vital signs (pulse rate, respiratory rate, supine blood pressure) will be taken as part of the screening visit and at the following time points:

- Florbetapir F18 Imaging Visit
 - Prior to injection of florbetapir F 18
- ^{18}F -AV-1451 Imaging Visit
 - Prior to the administration of ^{18}F -AV-1451 Injection
 - Within 5 minutes after completion of injection of ^{18}F -AV-1451 Injection
 - After the completion of imaging, prior to discharge.

Height and Weight

At both the screening visit and imaging visit (prior to ^{18}F -AV-1451 and florbetapir F 18 administration) body weight will be measured, lightly clothed. Height will only be measured as part of the screening visit.

Electrocardiogram (ECG)

A resting 12-lead electrocardiogram will be recorded as part of the screening visit.

Volumetric MRI

If a volumetric MRI has not been performed as part of PFBHS within six months days of the ¹⁸F-AV-1451 PET imaging visit, a volumetric MRI is to be performed as part of this study’s screening assessments. The specific parameters for the MRI will be described in a separate document.

Clinical Laboratory Tests

Clinical laboratory evaluation will be performed at the site’s local laboratory as part of the screening visit.

Tests will include:

- **Hematology** (4 mL EDTA);
- **Chemistry** (8.5 mL blood);
- **Urinalysis** (10 mL, urine); and
- **Thiamine** (vitamin B1; 4.0 mL blood).

A list of analytes and reference range laboratory values will be provided by the site to Avid.

Mini-Mental State Examination (MMSE)

The MMSE (Folstein et al., 1975) is a brief instrument used to assess cognitive function in elderly patients. The instrument is divided into 2 sections. The first section measures orientation, memory, and attention. The maximum score for the first section is 21. The second section tests the ability of the patient to name objects, follow verbal and written commands, write a sentence, and copy figures. The maximum score for the second section is 9. The range for the total MMSE score is 0 to 30. The MMSE will be assessed during the screening visit.

Digit span forward and backward (Wechsler Memory Scale-Revised (WMS-R))

Digit Span is composed of two tasks administered independently of each other: Digits Forward and Digits Backward. On both tasks, the examiner reads a series of number sequences to the subject. For each Digits Forward item, the subject is required to repeat the number sequence in the same order as presented. For Digits Backward, the subject is required to repeat the number sequence in the reverse order.

Beck Depression Inventory-II

The Beck Depression Inventory-II (Beck, Steer and Brown, 1996) is a 21-item, self-report rating inventory that measures characteristic attitudes and symptoms of depression.

Physician Visit

A physician must see the subject during the screening visit. A physician or a licensed/credentialed medical professional (i.e., a PET technologist, imaging center nurse or a regional equivalent) designated by the site principal investigator must assess or evaluate the subject prior to administration of ¹⁸F-AV-1451 Injection and prior to discharge from the imaging center. If a designee performs this activity, a physician must be available to provide medical consultation. A physician, or physician designee, must see the subject at baseline, prior to drug administration and at study end, prior to discharge from the florbetapir F 18 imaging session. At discharge, the physician or licensed/credentialed medical professional (or designee for the florbetapir F 18 imaging visit) should review all safety data and briefly examine/query the subject regarding potential adverse events or other treatment issues.

7.3 Protocol for Image Collection

The sponsor will prepare and distribute imaging manuals for ¹⁸F-AV-1451 and florbetapir F 18 image acquisition parameters and transmission procedures prior to site initiation.

7.4 Good Clinical Practice and Monitoring

All clinical studies performed under the direction of Avid/CRO will be conducted in accordance with applicable regulatory requirements and International Conference on Harmonization (ICH) Good Clinical Practice (GCP) and Avid/CRO Standard Operating Procedures (SOP).

This includes:

1. IRB approval: An investigation will be initiated at a study site only after the IRB for that study site has given their written approval of the protocol and informed consent;
2. Informed Consent: Study procedures will not be initiated until the subject signs the informed consent form;
3. Recording and monitoring of adverse events as outlined in Section 7.7.3 including the notification of study site clinical investigators, local IRBs and the FDA regarding serious adverse event;
4. Avid RP’s obligation to monitor the participating center on a regular basis; and
5. The termination of a center or the trial if conditions apply, as outlined in Section 5.6.

7.5 Informed Consent and Subject Information

Potential subjects will be allowed to read a written informed consent form. The principal investigator or designee will explain all study procedures, risks, and alternative therapies. The subject will have an opportunity to have all questions answered by a physician. The subject will then sign and date the informed consent form, indicating willingness to participate in the study.

If the subject is not capable of giving consent, consent may be given by a legally authorized representative. However, it is expected that all subjects entering this study should at least have the capacity to understand that they are engaging in a research study and should affirm that they do not object to participating, by signing on the Subject Assent line of the consent form. If the legal guardian is also the informant, the guardian must still sign the informant line of the form, indicating their own willingness to participate as an informant.

All informed consent forms must be approved by Avid or designee, and by the appropriate Institutional Review Board (IRB). No study related procedures shall be performed prior to completion of the informed consent process, and signing of the consent form. A copy of the signed informed consent should be given to the patient for their records.

7.6 Documentation

¹⁸F-AV-1451 and florbetapir F 18 PET scans will be saved in an appropriate electronic format as specified in the imaging manuals. A copy of all scans, including the MRI scans conducted per PFBH study protocol, will be saved at the site/imaging center and a copy of each will be forwarded to the sponsor described in the imaging manuals. All other data required by the protocol will be recorded in the eCRFs. All data in the eCRFs will be substantiated by “source documents,” which consist of the subject’s medical files, laboratory result sheets, ECG tracings, etc. All source documentation must be available to Avid, and its designees. Completed source documents and eCRFs may need to be made available and complete for an audit by the FDA, other international regulatory authorities, or Avid at any time. The eCRFs and all other records must be filed in accordance with applicable laws and regulations (see Section 10.6).

7.7 Adverse Events (AE)

Avid’s standards for recording and reporting adverse events (AEs) are to be followed regardless of applicable regulatory requirements that may be less stringent. All AEs must be fully recorded on the adverse event eCRFs. Investigators will be instructed to report to Avid, or its designee, their assessment of the potential relatedness of each AE to study drug or protocol procedure via electronic data entry. If a patient’s treatment is discontinued as a result of an AE,

study site personnel must clearly report to Avid, or its designee, via electronic data entry the circumstances and data leading to any such discontinuation of treatment. In cases where the investigator notices an unanticipated benefit to the patient, study site personnel should report “unexpected benefit” with the actual event term to Avid, or its designee (for example, the complete actual term would be “unexpected benefit- sleeping longer”).

Laboratory test abnormalities considered by the Investigator to be clinically relevant should be reported on the adverse event eCRFs. Signs and symptoms of each AE should be described in detail (e.g., start and stop dates/time, severity/intensity, relationship to study drug, action taken, and event resolution). Additionally, any clinically significant findings from laboratory evaluations, vital sign measurements, or other study procedures including those that result in a diagnosis should be reported as an AE to Avid, or its designee.

7.7.1 Adverse Event Monitoring

Each patient must be carefully monitored for adverse events. This includes clinical laboratory test variables. An assessment must be made of the severity/intensity and relationship to the administration of the study drug.

7.7.2 Adverse Event Definitions

Adverse Events

An adverse event is any undesirable experience occurring to a subject during a clinical trial, whether or not considered related to the study drug.

For reporting purposes, Avid will distinguish among pre-existing conditions, trial-emergent adverse events and treatment-emergent adverse events.

Pre-existing conditions (i.e., undesirable experiences, signs or symptoms that begin prior to the Screening Visit) will be recorded on the medical history eCRF pages. During the study, site personnel will record any change in the condition(s) and occurrence and nature of any AEs. Signs and symptoms that are believed to be due to the pre-existing condition(s) (started prior to dose of study medication) do not have to be recorded in the AEs section of the eCRF, unless there is an increase in frequency and severity.

Trial-emergent adverse events are undesirable experiences, signs or symptoms that begin, or worsen in intensity or frequency, after the informed consent, and prior to administration of the study drug at the imaging visit. Adverse events that occur between the florbetapir F 18 and the ¹⁸F-AV-1451 PET scans outside the 48 hour windows will also be considered trial-emergent adverse events. These will be recorded on the adverse event eCRFs.

Treatment-emergent adverse events are any untoward medical occurrence associated with the use of a drug in humans, whether or not considered drug related. For the purposes of this study, untoward medical occurrences will be considered associated with the use of ^{18}F -AV-1451, and thus be reported as adverse events, if they occur within 48 hours after ^{18}F -AV-1451 administration. Untoward medical occurrences will be considered associated with the use of Florbetapir F 18 Injection, if they occur within 48 hours after Florbetapir F 18 Injection administration.

The end of study, for the purpose of adverse event reporting, is defined as 48 hours after the last study drug administration (^{18}F -AV-1451 or Florbetapir F 18 Injection).

Serious Adverse Event (SAE)

A SAE is an AE that results in one of the following outcomes or constitutes one of the following events:

- Death;
- Initial or prolonged inpatient hospitalization (other than that required by protocol; “social hospitalization” or any hospitalization for non-medical reasons does not constitute a SAE);
- A life-threatening experience (that is, immediate risk of dying);
- Persistent or significant disability/incapacity;
- Congenital anomaly/birth defect;
- Considered significant by the investigator for any other reason.

Important medical events that may not result in death, be life-threatening, or require hospitalization may be considered serious adverse drug events when, based upon appropriate medical judgment, they may jeopardize the patient and may require medical or surgical intervention to prevent one of the outcomes listed in this definition.

Unexpected Adverse Event

An unexpected adverse event is an adverse event not previously reported or an adverse event that occurs with specificity, severity or frequency that is not consistent with the current IB.

Relationship to Study Drug

Investigators will be instructed to report their assessment of the potential relatedness of each adverse event to protocol procedure or study drug. The assessment of the relationship of an adverse event to the administration of the study drug is a clinical decision based on all available information at the time of the completion of the eCRF.

Intensity/Severity of an Adverse Event

In addition to assessing the relationship of the administration of the study drug to adverse events, an assessment is required, in order to determine the intensity (severity) of the event.

The following classifications should be used:

Mild:

A mild adverse event is an adverse event, usually transient in nature and generally not interfering with normal activities.

Moderate:

A moderate adverse event is an adverse event that is sufficiently discomforting to interfere with normal activities.

Severe:

A severe adverse event is an adverse event that incapacitates the subject and prevents normal activities. Note that a severe event is not necessarily a serious event; nor must a serious event necessarily be severe.

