10.7 Adverse Events

All adverse events encountered during the clinical trial must be documented on the eCRF, whether or not considered drug-related.

Eli Lilly must be notified immediately (as soon as possible, and in all cases within 24 hours) of a drug experience, condition, development, or event, which is considered serious. Eli Lilly must be notified immediately of any findings with the use of the drug that may suggest significant hazards, contraindications, adverse drug reactions (ADRs) and precautions pertinent to the safety of the drug. The investigator will be requested to complete a separate report form in addition to the information on the eCRF. See section 7.7.4 for reporting serious adverse events

If a SAE is determined to be unexpected (not previously reported or described by Avid), and study drug-related, Eli Lilly will notify the investigator in writing. The investigator should forward this notification to the IRB within 24 hours of receipt.

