11.2. Adverse Events

An AE is any undesirable experience occurring to a subject during a clinical trial, whether or not considered related to the study drug.

Treatment-emergent adverse events (TEAE) are any untoward medical occurrence associated with the use of a drug in humans, whether or not considered drug related. For the purposes of this study, untoward medical occurrences will be considered associated with the use of flortaucipir or florbetapir, and thus be reported as AEs, if they occur within 48 hours after administration of the respective PET tracer. AE that occur after the administration of study drug but outside the 48 hour reporting window will not be reported unless the investigator believes they are attributable to the drug.

The end of study for the purpose of AE reporting is defined as 48 hours after the administration of flortaucipir injection or florbetapir injection (whichever occurs last).

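### Protocol 7.7.2 asks more before a worsened pre-existing symptom must be recorded after injection than before it, so some non-serious worsening may be missing from the TEAE tables

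*Protocol*

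**What the plan says.** Protocol 7.7.2 sorts events into pre-existing conditions, trial-emergent events and treatment-emergent events (TEAEs).

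- **Pre-existing conditions.** These are experiences, "signs or symptoms that begin prior to the Screening Visit", and they go on the medical history pages. Symptoms attributed to them "do not have to be recorded in the AEs section of the eCRF, unless there is an increase in frequency and severity". That sentence also carries a qualifier on timing, "started prior to dose of study medication". Sites are also told to note changes in such conditions, but no eCRF page is named for this.
- **Trial-emergent events.** These "begin, or worsen in intensity or frequency, after the informed consent, and prior to administration of the study drug at the imaging visit". They go on the AE pages.
- **TEAEs.** These are untoward occurrences in the 48 hours after either tracer. Worsening is not mentioned. SAP 11.2 repeats the rule: events count "if they occur within 48 hours after administration of the respective PET tracer".

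On output, SAP 11.2.1 puts all AEs in a listing, and the tables in SAP 11.2.2 onward contain TEAEs only. Protocol 10.7 states the general duty: "All adverse events encountered during the clinical trial must be documented on the eCRF, whether or not considered drug-related".

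**The concern.** The exemption joins frequency and severity with *and*; the trial-emergent paragraph joins intensity and frequency with *or*. The *or* rule stops at injection, which is when a tracer or procedure effect first becomes possible. The threshold for recording therefore rises just as the safety question begins.

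The stake is the secondary objective of expanding the safety database. About 20 of the 30 planned subjects are to be enrolled with cognitive impairment, which under Protocol 5.3.1 may rest on subjective complaints alone. Pre-existing symptoms will thus be common, and a change in one of them is a plausible form for a post-dose event. Two sites could also handle the same event differently and both comply.

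**Working it through.** The documents give no figure on this point, so the check is a comparison of texts. Take a symptom attributed to a pre-existing condition and follow it through the rules.

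1. **Severity alone, or frequency alone, rises before the first injection.** The trial-emergent paragraph makes this an AE. The exemption, which has no time limit, says that it need not be recorded. The two sentences conflict.
2. **Severity alone, or frequency alone, rises within 48 hours after injection.** The trial-emergent paragraph's worsening clause no longer applies, and the TEAE paragraph is silent on worsening. The exemption is the only sentence that sets a threshold, and one dimension does not meet it. No AE entry is required. An event that is not entered is absent from both the TEAE tables and the all-AE listing.
3. **Both rise after injection.** An AE entry is required. Whether it becomes a TEAE depends on the onset date entered. If the time of worsening is entered, it falls inside the 48 hours. If the original onset is entered, it falls before injection. Neither document says which to use.
4. **The worsening is serious, or is a clinically significant laboratory, vital-sign or procedure finding.** Protocol 7.7 and 7.7.4 have separate reporting text for these.
5. **The worsening is thought to come from the tracer or procedure.** It is then not attributed to the old condition, and the exemption does not apply.

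Case 2 against case 1 is the inconsistency. Case 3 is the dating gap.

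**Does Appendix I 1.2 of the SAP settle the date?** Its onset rows are partial and missing only; there is no row for a complete onset date. A missing onset, or a partial one that could fall in the window, is treated conservatively: a stop at or after injection, or no stop date, makes the event a TEAE. A partial onset that clearly precedes injection is not a TEAE. No row considers a date of worsening.

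**Does the note of a change reach an output by another route?** The trial flow chart schedules medical history at screening only. The listing in SAP 9.2 has class, condition, start and end dates and whether the condition is still present. It has no field for severity or change. A change noted there would appear in no planned safety summary.

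**Two cut-offs.** One sentence places pre-existing onset before the Screening Visit; the qualifier in the exemption places it before dosing. Protocol 5.1 allows up to 90 days between screening and the scan, and longer with sponsor approval. A symptom that starts in that interval and is attributed to an older condition is recordable under one sentence and exempt under the other. It is pre-dose, so this affects the all-AE listing and not the TEAE tables.

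**The case against.** The case on the other side has real force.

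- **The exemption is narrow and permissive.** It covers only symptoms attributed to the old condition, allows omission without requiring it, and lapses when both dimensions rise. Worsening that the investigator suspects is due to the tracer is outside it. This stands, and it confines the risk to one-dimension worsening that is attributed, perhaps wrongly, to the old condition.
- **The general texts are broad.** The AE definition and the TEAE wording are wide enough to include worsening, and Protocol 7.7, 7.7.3 and 10.7 require all AEs to be recorded. This stands as far as it goes: silence on worsening is an omission, not a contradiction. It does not remove the problem, because a specific exemption beside a general duty still lets a site leave the event out.
- **Other safeguards exist.** Serious events have their own reporting rule, and vital-sign changes are tabulated under SAP 11.3 and 11.4 whether or not an AE is entered. This also stands. A non-serious reported symptom is not clearly caught by either.

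A reader might infer that all post-dose worsening disappears from the safety tables. Cases 3 to 5 show that it does not. A reader might also infer that Appendix I 1.2 rules out any event with a known pre-dose onset. It does not govern complete dates; the supportable statement is that a rule for worsened conditions is missing.

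**Conclusion.** The inconsistency is real and limited. Non-serious post-dose worsening in severity alone or frequency alone, when attributed to a pre-existing condition, need not be entered as an AE and may be missing from the TEAE tables. The silence of both TEAE definitions on worsening and the lack of an onset rule add uncertainty for events that are entered. The two cut-offs make the all-AE listing inconsistent.

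The conclusion rests on reading *and* literally and on sites using the permission that they are given. For case 2 the effect is in one direction: the exemption can only reduce the AE count.

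Its size cannot be derived. It is tempting to use 20/30 = 67% of subjects with impairment, or 1/30 = 3.3 percentage points per subject with an event, as a measure. The first counts subjects who may have pre-existing complaints, not subjects who lose an event. The second is the weight of any one subject in a study of 30. Neither estimates lost events.

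The effect is on descriptive safety summaries, with no statistical comparison planned (SAP 11). The imaging analyses are unaffected. The wording should be corrected because the correction is cheap, not because a large loss has been shown.

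**What to change.** In Protocol 7.7.2:

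- Change the exemption so that an increase in frequency *or* severity ends it, in line with the trial-emergent paragraph.
- Use one cut-off for pre-existing conditions throughout. The Screening Visit cut-off is already in the definition.
- Add worsening in intensity or frequency to the treatment-emergent definition.

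In the SAP:

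- Carry the same TEAE wording into 11.2.
- State in 11.2 and Appendix I 1.2 that, for a worsened condition, the date and time of worsening is the onset for TEAE classification.

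The cost is a wording amendment to one protocol section and matching sentences in the SAP, a few more AE entries, and possibly a slightly higher TEAE count. No procedure or visit is added. The protocol change is the one that matters for case 2: a SAP change alone cannot recover an event that was never entered.
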